2.4.3.2 Enteral Nutritional Intake

Nutrition from formula, breast milk, nutritional shakes, fortifiers, MCT oil, and other enteral intakes are recorded on the CRF. The below data will be calculated and summarized by treatment group. Similarly, all enteral nutrition given on each day will be added together and summarized by treatment group. If weight on that day is missing, then the weight from the prior non-missing day will be used. If the patient had multiple records of the same intake (i.e. 2 different records of breastmilk with no fortifier) on the same day, then the records should be summed together to get the total in a 24 hour period. All units presented below for intake are in mL. If data is given in ounces, multiply the amount of ounces by 29.57 to get mL.

Breastmilk or formula (no additive or fortifier):

Fluid intake ordered (mL/kg/24 hours):

 $\frac{Total \ volume \ ordered \ (mL)}{Weight \ on \ that \ day \ (kg)}$

If total volume ordered is recorded in ml/3 hours, then the amount should be multiplied by 8 to find the total volume ordered in mL per 24 hours. If total volume ordered is recorded in ml/2 hours, then the amount should be multiplied by 12.

Fluid intake administered (mL/kg/24 hours):

Total volume received (mL) Weight on that day (kg)

Energy intake ordered (kCal/kg/24 hours):

Original kcal in formulation per mL * Total Volume Ordered (mL) Weight on that day (kg)

Energy intake administered (kCal/kg/24 hours):

Original kcal in formulation per mL * Total Volume Received (mL) Weight on that day (kg)

Protein intake ordered (g/kg/24 hours):

Total Volume Ordered (mL) * Protein Conversion from Table 2 Weight on that day (kg)

Protein intake administered (g/kg/24 hours):

Total Volume Received (mL) * Protein Conversion from Table 2 Weight on that day (kg)

Carbohydrate intake ordered (g/kg/24 hours):

Total Volume Ordered (mL) * Carbohydrate Conversion from Table 2 Weight on that day (kg)

Carbohydrate intake administered (g/kg/24 hours):

Total Volume Received (mL) * Carbohydrate Conversion from Table 2 Weight on that day (kg) Lipid intake ordered (g/kg/24 hours):

Total Volume Ordered (mL) * Lipid Conversion from Table 2 Weight on that day (kg)

Lipid intake administered (g/kg/24 hours):

Total Volume Received (mL) * Lipid Conversion from Table 2 Weight on that day (kg)

Protein	Carbohydrate	Lipid
0.012 g/mL	0.074 g/mL	0.036 g/mL
0.019 g/mL	0.074 g/mL	0.034 g/mL
0.033 g/mL	0.122 g/mL	0.044 g/mL
0.014 g/mL	0.076 g/mL	0.036 g/mL
0.019 g/mL	0.069 g/mL	0.038 g/mL
0.024 g/mL	0.083 g/mL	0.044 g/mL
0.021 g/mL	0.075 g/mL	0.041 g/mL
0.052 g/mL	0.16 g/mL	0.068 g/mL
0 g/mL	0.028 g/mL	0 g/mL
	Protein 0.012 g/mL 0.019 g/mL 0.033 g/mL 0.014 g/mL 0.019 g/mL 0.019 g/mL 0.019 g/mL 0.019 g/mL 0.019 g/mL 0.021 g/mL 0.052 g/mL 0 g/mL	Protein Carbohydrate 0.012 g/mL 0.074 g/mL 0.019 g/mL 0.074 g/mL 0.033 g/mL 0.122 g/mL 0.014 g/mL 0.076 g/mL 0.019 g/mL 0.069 g/mL 0.019 g/mL 0.069 g/mL 0.019 g/mL 0.069 g/mL 0.019 g/mL 0.069 g/mL 0.021 g/mL 0.075 g/mL 0.052 g/mL 0.16 g/mL 0 g/mL 0.028 g/mL

Table 2. Conversion Factors

Breastmilk or formula (with additive or fortifier): The amount of additive/fortifier received will need to be calculated and used in the formulas. It can be calculated as:

 $\frac{Total \ Quantity \ Ordered \ (mL)}{Total \ Volume \ Ordered \ In(mL)} * Total \ Volume \ Received \ (mL)$

Fluid intake ordered (mL/kg/24 hours):

 $\frac{Total \ volume \ ordered \ (mL) + Total \ volume \ ordered \ of \ additive \ (mL)}{Weight \ on \ that \ day \ (kg)}$

If total volume ordered is recorded in ml/3 hours, then the amount should be multiplied by 8 to find the total volume ordered in mL per 24 hours. If total volume ordered is recorded in ml/2 hours, then the amount should be multiplied by 12.

Fluid intake administered (mL/kg/24 hours):

 $\frac{Total \ volume \ received \ (mL) + Total \ volume \ of \ additive/fortifier \ (mL)}{Weight \ on \ that \ day \ (kg)}$

Energy intake ordered (kCal/kg/24 hours):

Modified kcal in formulation per mL * Total Volume Ordered (mL) Weight on that day (kg)

Energy intake administered (kCal/kg/24 hours):

Modified kcal in formulation per mL * Total Volume Received (mL) Weight on that day (kg)

Protein intake ordered (g/kg/24 hours):

 $Protein intake ordered from 2.4.3.2 + \frac{Total Volume Ordered of Additive(mL, packet, or g) * Protein Conversion from Table 3}{Weight on that day (kg)}$

Protein intake administered (g/kg/24 hours):

Protein intake administered from 2.4.3.2 + $\frac{Total Volume Received of Additive(mL, packet, or g) * Protein Conversion from Table 3}{Weight on that day (kg)}$

Carbohydrate intake ordered (g/kg/24 hours):

Carb intake ordered from 2.4.3.2 + $\frac{Total Volume Ordered of Additive(mL, packet, or g) * Carb Conversion from Table 3}{Weight on that day (kg)}$

Carbohydrate intake administered (g/kg/24 hours):

Carb intake administered from 2.4.3.2 + $\frac{Total Volume Received of Additive(mL, packet, or g) * Carb Conversion from Table 3}{Weight on that day (kg)}$

Lipid intake ordered (g/kg/24 hours):

Lipid intake ordered from 2.4.3.2 + $\frac{Total Volume Ordered of Additive(mL, packet, or g) * Lipid Conversion from Table 3}{Weight on that day (kg)}$

Lipid intake administered (g/kg/24 hours):

Lipid intake administered from 2.4.3.2

+ Total Volume Ordered of Additive(mL, packet, or g) * Lipid Conversion from Table 3 Weight on that day (kg)

Additive/Fortifier	Protein	Carbohydrate	Lipid
Enfamil liquid HMF ¹³	0.084 g/mL	0.056 g/mL	0.116 g/mL
Similac HMF Concentrated Liquid ¹⁴	0.07 g/mL	0.162 g/mL	0.054 g/mL
^A Similac Hydrolyzed HMF ¹⁵	0.5 g/packet	0.75 g/packet	0.21 g/packet
Similac Neosure Powder ¹⁶	0.021 g/mL	0.075 g/mL	0.041 g/mL
Pregestimil Powder ⁸	0.019 g/mL	0.069 g/mL	0.038 g/mL
Prolacta $+4^{17}$	0.06 g/mL	0.095 g/mL	0.095 g/mL
^A Similac HMF Powder ¹⁸	0.25 g/packet	0.45 g/packet	0.09 g/packet
^A Neocate Infant Powder ¹⁹	0.135 g/g	0.52 g/g	0.245 g/g

Table 3. Additive and Human Milk Fortifier (HMF) Conversions

^AFor all additives given as powder (g or packets), the volume of this additive is assumed to be 0 for fluid intake calculations.

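### SAP 2.4.3.2 puts energy and the other fortified-feed intakes on different volume bases, and two powder rows in Table 3 carry prepared-formula values

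*SAP*

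**What the plan says.** SAP 2.4.3.2 has one set of formulas for breast milk or formula given alone and another for feeds with an additive or fortifier.

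- **Energy, plain feed:** "Original kcal in formulation per mL * Total Volume Received (mL", over weight.
- **Energy, fortified feed:** "Modified kcal in formulation per mL * Total Volume Received (mL" for the amount administered and "Modified kcal in formulation per mL * Total Volume Ordered (mL" for the amount ordered, each over weight. Neither has an additive term.
- **Fluid, fortified feed:** total volume plus the volume of additive, over weight.
- **Macronutrients, fortified feed:** the plain-feed intake (for protein, "Protein intake administered from 2.4.3.2", which is Total Volume times a Table 2 factor) plus additive amount times a Table 3 factor.
- **Additive received:** "The amount of additive/fortifier received will need to be calculated and used in the formulas". It is prorated from the ordered quantity by the volume received.

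Neither Total Volume nor the modified kcal/mL is defined.

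Table 3 lists eight additives. Three powders, given per gram or per packet, carry a footnote under which "the volume of this additive is assumed to be 0 for fluid intake calculations". The rows for "Similac Neosure Powder" (0.021 / 0.075 / 0.041 g/mL protein / carbohydrate / lipid) and Pregestimil Powder (0.019 / 0.069 / 0.038 g/mL) are per mL and do not carry that footnote.

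**The concern.** Adding the additive to Total Volume, as fluid and macronutrients do, makes sense only if Total Volume excludes it. Multiplying a mixed-feed density by Total Volume, as energy does, makes sense only if Total Volume includes it. The change of label from original to modified kcal/mL between the plain and fortified formulas points to a mixed-feed density.

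The two powder rows are a separate matter: products named as powders have the composition of a ready-to-feed liquid.

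Nutritional adequacy is a named secondary endpoint. Enteral energy feeds overall energy and the PN and EN percentages in SAP 2.4.3.4. SAP 1.4.2 gives the purpose as reference data and descriptive summaries, so the absolute values are themselves the product, and an error common to both arms does not cancel out of them. The criterion on the PN share of energy applies at Screening only (Protocol 5.6.3), so enteral feeding may grow during treatment.

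**Working it through.** The SAP states no result to reproduce here, so the check puts one feed through its formulas.

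**Inputs from the SAP** (protein / carbohydrate / lipid)
- Base feed: Table 2, first row, 0.012 / 0.074 / 0.036 g/mL. Row labels are missing from the text available to me. The nine rows follow the order of references 4 to 12, which makes the first row human milk.
- Enfamil liquid HMF: Table 3, 0.084 / 0.056 / 0.116 g/mL.

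**Assumptions, not in the documents**
- 4 / 4 / 9 kcal per g for protein / carbohydrate / lipid.
- Mixing ratio: 20 mL additive per 100 mL base, with 5 to 25 mL as the range.

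**Step 1. Energy in the feed**
- Base: 4(0.012) + 4(0.074) + 9(0.036) = 0.668 kcal/mL; 100 mL gives 66.8 kcal.
- Additive: 4(0.084) + 4(0.056) + 9(0.116) = 1.604 kcal/mL; 20 mL gives 32.1 kcal.
- Total 98.9 kcal in 120 mL, a mixed density of 0.824 kcal/mL.

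**Step 2. The SAP formulas under each meaning of Total Volume**

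| Quantity | In the feed | Total Volume = base (100 mL) | Total Volume = prepared feed (120 mL) |
|---|---|---|---|
| Energy, kcal | 98.9 | 0.824 × 100 = 82.4 (−16.7%) | 0.824 × 120 = 98.9 |
| Fluid, mL | 120 | 100 + 20 = 120 | 120 + 20 = 140 (+16.7%) |
| Protein, g | 2.88 | 1.20 + 1.68 = 2.88 | 1.44 + 1.68 = 3.12 (+8.3%) |
| Carbohydrate, g | 8.52 | 7.40 + 1.12 = 8.52 | 8.88 + 1.12 = 10.00 (+17.4%) |
| Lipid, g | 5.92 | 3.60 + 2.32 = 5.92 | 4.32 + 2.32 = 6.64 (+12.2%) |

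With a mixed-feed density, neither column is right throughout.

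**Step 3. Range.** With a mL of additive per 100 mL base, the energy shortfall in the base-feed column is a/(100+a), whatever the liquid fortifier: 4.8% at 5 mL, 9.1% at 10 mL, 16.7% at 20 mL, 20% at 25 mL. In the prepared-feed column fluid is over by the same fraction. Over the three liquid fortifiers and ratios of 10 to 25 mL, macronutrients are over by about 6% to 21%.

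**Step 4. PN share, illustrated.** Suppose PN truly supplies 80% of energy and liquid-fortified feed the other 20%. A 16.7% shortfall turns 20 into 16.7. The total falls to 96.7 (−3.3%) and the PN share reads 80/96.7 = 82.8%.

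**Step 5. Which additives.** The conflict affects Enfamil liquid HMF, Similac HMF Concentrated Liquid, Prolacta +4, and Neosure and Pregestimil as listed in mL. The three footnoted powders have zero volume, so base and prepared volumes coincide and there is no conflict.

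**Step 6. The two powder rows**
- The Neosure and Pregestimil values equal the seventh and fifth rows of Table 2 on all three nutrients. By order those rows belong to references 10 (Neosure) and 8 (Pregestimil), and Table 3 itself cites reference 8 for Pregestimil.
- Neosure: 4(0.021) + 4(0.075) + 9(0.041) = 0.753 kcal/mL. Pregestimil: 4(0.019) + 4(0.069) + 9(0.038) = 0.694 kcal/mL. Added to milk at 0.668 kcal/mL, no amount could lift the mixture above those figures.
- The one powder given per gram, Neocate (0.135 / 0.52 / 0.245 g/g), has 4(0.135) + 4(0.52) + 9(0.245) = 4.825 kcal/g.
- Neocate factor over listed factor, by nutrient: Neosure 6.4, 6.9, 6.0; Pregestimil 7.1, 7.5, 6.4. These apply only if grams are recorded and Neocate is typical.
- If mL of dry powder is recorded, an assumed 0.4 to 0.6 g/mL gives an energy-equivalent ratio of 2.6 to 4.2.

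**The case against.** The strongest reply is that this is a gap in definitions, not an error of known direction. Total Volume is undefined, and density times volume reads naturally as mixture times mixture, in which case energy is right. The rule for prorating the additive does not settle it, since it works on either basis. This stands: a reader might infer that enteral energy is understated, and the documents do not establish that.

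A reader might also infer that the formulas conflict under any definition. They do not. If the modified kcal/mL were expressed per mL of base feed, the example gives 98.9/100 = 0.989 kcal/mL, and 0.989 × 100 = 98.9 kcal, so energy, fluid and macronutrients agree. That is a less natural meaning, but the SAP does not exclude it.

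On the powders, section 2.4.3.2 says its intakes are in mL, and the footnote covers powders given in grams or packets. The missing flag therefore fits an mL entry. If mL of prepared formula is recorded, the factors may be right and only the word powder is wrong. The 6- to 7.5-fold figure is therefore conditional. Nor do the Table 3 factors misstate energy, which uses the modified kcal/mL.

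Finally, the endpoint is descriptive, both arms share the formulas, and the documents do not say how many infants receive liquid fortifier. These points limit the weight of the issue. They do not remove the need to choose a basis: with a mixed-feed density, the SAP as written gives a wrong value somewhere.

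**Conclusion.** The inconsistency is real for additives with a counted volume, provided the modified kcal/mL means mixed-feed density, which is its natural reading. Its direction depends on what the eCRF records:

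- **Base feed:** energy is understated by 4.8% to 20% over the assumed ratios, and the PN share of energy is overstated.
- **Prepared feed:** energy is right, fluid is overstated by the same 4.8% to 20%, and protein, carbohydrate and lipid are overstated as well.

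The two Table 3 powder rows repeat prepared-formula values under a powder label. Whether the factors or the label are wrong depends on the recorded unit, and the consequence is for macronutrients and fluid only.

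The impact is confined to the descriptive secondary endpoint of nutritional adequacy, and the Holman Index does not depend on it. It should be corrected, because the formulas as written do not give one coherent account of intake.

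**What to change.** 1. From the eCRF, define Total Volume (base or prepared feed) and modified kcal/mL (per mL of mixture or of base) in SAP 2.4.3.2.
2. Put all fortified-feed formulas on that basis, for both ordered and received amounts.
   - Base feed with mixed-feed density: energy = modified kcal/mL × (base + additive volume), or base energy plus additive energy.
   - Prepared feed with mixed-feed density: leave energy as it is, drop the added volume from fluid, and apply the Table 2 factors to Total Volume minus additive volume.
   - Base feed with density per mL of base: leave the formulas and state the definitions.
3. Do not add the additive volume to energy before step 1 is settled. If prepared volume is recorded, the example would become 140/120, an overstatement of 16.7%.
4. Confirm the recorded unit for Neosure and Pregestimil. If grams, replace both rows with per-gram values and flag them as zero volume. If mL of prepared formula, correct the powder label. If mL of dry powder, new factors are needed.
5. In the same edit, correct lipid administered with an additive. It uses the ordered additive amount, where protein and carbohydrate use the received amount.

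The cost is a SAP edit to formulas and one table, plus reprogramming. No new data are needed if the eCRF already records the volume basis and units; otherwise, a site query.

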6.9 Nutritional Intake

Prescribed and actual macronutrient intake (fluid, energy, protein, carbohydrates, and lipid) of both parenteral and enteral nutrition will be collected and recorded on a daily basis in the CRF from Baseline to end of study treatment for each of the treatment groups. See Appendix 1, Schedule of Events Table, for additional details.

Intravenous intakes (fluid, amino acid, dextrose/glucose, and lipid) from PN as well as any intravenous macronutrient additions to the PN solution will be collected and recorded as parenteral intakes.

For breast milk intake, the macronutrient content will be estimated from volume intakes using mean reference values in mature human milk (640 kcal, 12 g of protein, 67 g of carbohydrates, and 34 g of lipid per 1 Liter of milk).²³ When breastfeeding intakes cannot be measured, the best estimation (volume) of the investigator will be recorded. For commercial products including formula and human milk fortifiers, macronutrient intakes will be recorded from volume intake and calculated from manufacturer label. For oral food ingestion, energy and lipid intakes only will be recorded from best estimates.

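### For feeds with a lipid-containing additive, the SAP computes lipid administered from the additive ordered instead of received, which overstates enteral lipid when such a feed is only partly taken

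*SAP*

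**What the plan says.** SAP 2.4.3.2 treats feeds with an additive or fortifier in their own block. It opens with a rule: "The amount of additive/fortifier received will need to be calculated and used in the formulas". The equation that follows is additive ordered divided by feed volume ordered, times feed volume received.

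The three administered-macronutrient formulas in that block then use these additive terms:

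- Protein: "Total Volume Received of Additive(mL, packet, or g) * Protein Conversion from Table 3"
- Carbohydrate: "Total Volume Received of Additive(mL, packet, or g) * Carb Conversion from Table 3"
- Lipid: "Total Volume Ordered of Additive(mL, packet, or g) * Lipid Conversion from Table 3"

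The lipid term is the one used for lipid ordered, immediately above: "Total Volume Ordered of Additive(mL, packet, or g) * Lipid Conversion from Table 3}{Weight on that day (kg". For feeds without an additive, the administered-lipid formula uses the volume received: "Total Volume Received (mL) * Lipid Conversion from Table 2 Weight on that day (kg".

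On a related matter, Protocol 6.9 fixes the composition of breast milk at "640 kcal, 12 g of protein, 67 g of carbohydrates, and 34 g of lipid per 1 Liter of milk". The first row of SAP Table 2 reads "0.012 g/mL 0.074 g/mL 0.036 g/mL" for protein, carbohydrate and lipid. SAP section 3 declares no departure from the protocol's analyses.

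**The concern.** Prescribed and actual lipid intake, from enteral as well as parenteral sources, is part of the secondary endpoint on adequacy of nutrition (Protocol 2.2 and 9.6.2.1; SAP 1.6.2 and 2.4.3). The purpose of tabulating both is to show how far delivery fell short of the order. With the formula as printed, an infant who takes part of a fortified feed is credited with all the fat in the fortifier. For lipid alone among the three macronutrients, the additive contributes nothing to the difference between ordered and administered.

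A programmer following the SAP must either implement the slip or depart from the plan without a record. The affected outputs are the enteral intake table (14.3.6.4.2), the enteral macronutrient listing (16.2.11.2.4) and the box plots of administered enteral intake (14.3.6.4.2.2).

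**Working it through.** **Inputs from the documents.** Additive lipid factors a from SAP Table 3: 0.116, 0.095 and 0.054 g/mL for three liquid fortifiers, and 0.21 and 0.09 g per packet for two powders. Milk lipid factor m = 0.036 g/mL, the first row of SAP Table 2.

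**Assumptions.** The documents give no feed volumes, mixing ratios or fractions taken. I assume a 1 kg infant, V = 100 mL milk ordered, and A = 20 mL (25 mL for the 0.095 product) or 4 packets ordered. The fraction f of the feed received is varied.

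**Formulas.**

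- SAP as printed: (m·f·V + a·A)/weight
- SAP's own rule, with additive received = (A/V)·(f·V) = f·A: (m·f·V + a·f·A)/weight
- Excess: a·A·(1−f)/weight
- Relative excess: s·(1−f)/f, where s = a·A/(m·V + a·A) is the additive's share of the lipid ordered. Weight cancels.

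**One case in full** (a = 0.116, A = 20 mL, f = 0.5):

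- As printed: 0.036·50 + 0.116·20 = 1.80 + 2.32 = 4.12 g/kg
- By the rule: 0.036·50 + 0.116·10 = 1.80 + 1.16 = 2.96 g/kg
- Excess: 1.16 g/kg, or 4.12/2.96 − 1 = 39%

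**Across additives** (g/kg, as printed vs by the rule):

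| Additive lipid factor, amount | f = 0.75 | f = 0.50 | f = 0.25 |
|---|---|---|---|
| 0.095 g/mL, 25 mL | 5.08 vs 4.48 (+13%) | 4.18 vs 2.99 (+40%) | 3.28 vs 1.49 (+119%) |
| 0.116 g/mL, 20 mL | 5.02 vs 4.44 (+13%) | 4.12 vs 2.96 (+39%) | 3.22 vs 1.48 (+118%) |
| 0.054 g/mL, 20 mL | 3.78 vs 3.51 (+8%) | 2.88 vs 2.34 (+23%) | 1.98 vs 1.17 (+69%) |
| 0.21 g/packet, 4 | 3.54 vs 3.33 (+6%) | 2.64 vs 2.22 (+19%) | 1.74 vs 1.11 (+57%) |
| 0.09 g/packet, 4 | 3.06 vs 2.97 (+3%) | 2.16 vs 1.98 (+9%) | 1.26 vs 0.99 (+27%) |

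At f = 1 the excess is zero. At f = 0 the formula still credits the whole additive, 2.32 g/kg in the worked case. If more is given than ordered the sign reverses: at f = 1.1 the error is about −1% to −4%.

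**Effect on the shortfall.** In the worked case the lipid ordered is 100·0.036 + 20·0.116 = 5.92 g/kg. At f = 0.5 the printed formula shows a shortfall of (5.92 − 4.12)/5.92 = 30%, where the rule gives 50%. At f = 0.25 it shows 46% instead of 75%.

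**Human-milk factors, a separate check.** Protocol 6.9 converts to 0.012, 0.067 and 0.034 g/mL for protein, carbohydrate and lipid. No row of Table 2 has that set. Against the first row, protein agrees, carbohydrate is 0.074/0.067 = 1.104 (+10.4%) and lipid is 0.036/0.034 = 1.059 (+5.9%). The row labels are lost in the text available. I take the first row as human milk for two reasons. SAP references 4 to 12 are nine sources for nine rows, and the first is a human-milk composition study. The fifth and seventh rows also equal the Table 3 values of the products in references 8 and 10.

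**The case against.** The strongest reply is that the intended derivation is not in doubt. The block states the rule, the two sibling formulas follow it, and the lipid line looks copied from the ordered-lipid line above. That stands as an account of how the slip arose and is a reason to rate it modestly. It does not remove the need to correct the text, because the printed formula is what will be programmed and checked.

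The reach is also limited, and three stronger readings fail.

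- A reader might infer that enteral lipid is overstated whenever any feed is left unfinished. It is not. Feeds without an additive use volume received, so only a feed with a lipid-containing additive is affected.
- A reader might infer that the lipid shortfall is concealed. The base-feed term still uses volume received, so the shortfall shows but is too small.
- A reader might infer that the EFAD result is distorted. EFAD is derived from the Holman Index alone (SAP 2.4.1.1), there is no covariate adjustment (2.6.1), and no planned analysis relates enteral lipid to EFAD. Administered energy for fortified feeds uses volume received, and overall intake (2.4.3.4) sums only fluid and energy. The same formula applies in both arms.

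It is also fair to say that a single example with the 0.116 g/mL fortifier sits near the top of the range, which is why the table includes the low end.

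On the milk factors, the row identification is an inference, and the documents do not show which set is better. What stands is that the two documents differ and the SAP does not say so.

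**Conclusion.** The administered-lipid formula for fortified feeds is wrong as written, because it contradicts the SAP's own rule and the matching protein and carbohydrate formulas. For a feed with a lipid-containing additive that is only partly taken, administered enteral lipid is too high by a·A·(1−f)/weight. The direction follows from the formula. The size rests on the assumed mixes above: roughly 9% to 40% at half received and 3% to 13% at three quarters received. How often such feeds occur in the trial cannot be judged from the documents. The error stays within the enteral lipid outputs of one secondary endpoint, so it should be corrected but does not threaten the primary result.

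The human-milk factors are a distinct and smaller matter. If the first row of Table 2 is human milk, its lipid is 5.9% and its carbohydrate 10.4% above the protocol's values at any fraction taken, including a feed taken in full. This is an undeclared difference between the documents, not a consequence of the ordered-for-received slip.

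**What to change.** In SAP 2.4.3.2, in the administered-lipid formula for milk or formula with an additive, replace the additive volume *ordered* with the additive volume *received*, as in the protein and carbohydrate formulas. The lipid program and its outputs should then be checked against the corrected text.

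Separately, either set the human-milk row of Table 2 to the Protocol 6.9 values (0.012, 0.067 and 0.034 g/mL), or keep the SAP's factors and record the change, with its source, in SAP section 3.

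The cost is one word in a formula, plus one table row or one sentence, and the matching program edits. No new data are needed, since the received amount comes from quantities the SAP already uses.
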